The sponsor, participating sites and all investigators involved in the study shall treat all information and data related to the study as confidential and with the proper respect for the privacy of each participant. The parties shall equally warrant to not disclose such information to third parties or disclose such publicly, but shall use such information solely for the purpose of this study. All data shall be coded or de-identified prior to transfer of such data to sponsor.

Parties have expressly agreed that any and all data collected and prepared in the context of the study shall be the property of the sponsor, provided that the participating sites shall remain the owner of their source data and may utilize such data as it deems appropriate without the approval of sponsor.

The participating sites and their proper investigators warrant that they shall not perform the study without having obtained the proper, written informed consent from each participant, in accordance with applicable legislation and as approved by the appropriate ethics committee/review board.

16. References

¹MOORE TR, GALE S, BENIRSCHKE K. (1990) Perinatal outcome of forty-nine pregnancies complicated by acardiac twinning. *Am J Obstet Gynecol*.163. p.907-912.

²PAGANI G1, D'ANTONIO F, KHALIL A, PAPAGEORGHIOU A, BHIDE A, THILAGANATHAN B. (2013) Intrafetal laser treatment for twin reversed arterial perfusion sequence: cohort study and meta-analysis. *Ultrasound Obstet Gynecol.* 42. p.6-14.

⁴NICOLAIDES KH, BRIZOT M, PATEL F, SNIJDERS R. (1994) Comparison of chorionic villus sampling and amniocentesis for fetal karyotyping at 10–13 weeks' gestation. *Lancet*. 344. p.435–439.

⁵SUNDBERG K, BANG J, SMIDT- JENSEN S, BROCKS V, LUNDSTEEN C, PARNER J, KEIDING N, PHILIP J. (1997) Randomised study of risk of fetal loss related to early amniocentesis versus chorionic villus sampling. *Lancet*. 350. p.697–703.

⁶CEMAT GROUP. (1998) Randomised trial to assess safety and fetal outcome of early and mid-trimester amniocentesis. *Lancet*. 351. p.242–247.

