If the pump twin survives to 16 weeks and is treated thereafter, approximately 80% will survive⁸. However, a major disadvantage of delaying the intervention until after 16 weeks' gestation is the high mortality of the pump twin (up to 33%) between the diagnosis at 12 weeks and the planned intervention at 16 weeks⁹. These early demises are entirely unpredictable⁹. As such, the survival rate for TRAP diagnosed at 12 weeks and treated after 16 weeks is estimated to only about 50%⁸ ⁹. Also, a recent meta-analysis demonstrated an inverse relationship between gestational age at treatment and gestational age at birth, suggesting that an earlier intervention may decrease the risk of very preterm birth. An intervention at 12-14 weeks may thus prevent the early deaths and reduce the risk of very preterm birth, but might also increase the risk the miscarriage because of premature rupture of the membranes.

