Intact survival rate (proportion) defined as the number of surviving infants with normal development at two years of age corrected for prematurity as assessed by the ASQ® score for infant development. A score of more than 2 SD below the mean score for term-born children will be considered abnormal. Centers that have a follow-up scheme in place, may additionally report the Bayley III score¹⁸.

4.2. Description of the trial design.

We propose to conduct a multi-center open-label randomized controlled trial to assess if early intervention (12.0-14.0 weeks) (study group) improves the outcome of TRAP sequence as compared to late intervention (16.0-19.0 weeks) (control group). We will randomly assign women diagnosed with TRAP sequence diagnosed between 11.6 and 13.6 weeks (1:1) to an early or late intervention group, using a webbased application (www.sealedenvelope.com) with a computer-generated list with random permuted blocks of sizes 2 or 4, stratified by gestational age at inclusion (11.6 -12.6 weeks versus 13.0-13.6 weeks). Analysis will be by intention-to-treat. Outcome will be adjudicated blinded to group allocation.

4.3. Flowchart.

4.4. Description of the intervention.

All interventions will be done under local anaesthesia and/or conscious sedation in sterile conditions by an experienced operator. They must be performed within 1 week after randomisation and at the latest at 14.0 weeks in the early group and 19.0 weeks in the late group. In the early group, only intrafetal coagulation will be used. Intrafetal ablation will be performed under ultrasound guidance using an 18-gauge (1.27 mm) to 20-gauge (0.91 mm) needle with a free-hand technique. The needle is introduced into the pelvis/abdomen of the TRAP mass close to the intra-abdominal portion of the feeding vessel, while avoiding puncture of the placenta and pump twin sac. The procedure is considered successful when there is complete cessation of reverse flow into the TRAP mass on intraoperative color-flow mapping.

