We will use a web-based application (www.sealedenvelope.be) with a computer-generated list with random block sizes of two to four, stratified by gestational age at inclusion (12.0 -12.6 weeks versus 13.0-13.6 weeks). The investigators will be blinded to the randomization sequence.

4.7. Definition of what is considered to be the end of the study.

The study will end after assessing the neurodevelopmental outcome by the parent-completed Ages and Stages Questionnaire (ASQ®) at 2 years of age corrected for prematurity of the surviving children.

5. Selection and withdrawal of subjects

5.1. Inclusion criteria.

✓TRAP sequence in a monochorionic diamniotic twin pregnancy diagnosed between 11.6 and 13.6 weeks, as determined by the crown-rump length of the pump twin in spontaneous conceptions and by the date of insemination or embryonic age at replacement in pregnancies resulting from subfertility treatment

✓Women aged 18 years or more, who are able to consent

✓ Anatomically normal pump twin

✓ Provide written informed consent to participate in this RCT, forms being approved by the Ethical Committees

5.2. Exclusion criteria.

XContraindication for an intervention due to a severe maternal medical condition or threatening miscarriage XInaccessibility of the acardiac twin due to a retroverted uterus, severe maternal obesity, uterine fibroids, bowel or placental superposition

XA major anomaly in the pump twin, requiring surgery or leading to infant death or severe handicap XSpontaneous arrest of the reverse flow and/or pump twin demise at diagnosis

Patients diagnosed with TRAP sequence will be informed about the nature of the disease, the expected outcome and the possible management options including termination of pregnancy, expectant management and intrauterine intervention. Patients who opt for an intervention and who are eligible for participation will be invited by the fetal medicine specialist at the time of diagnosis. Patients that are not eligible or eligible but not willing to participate will be invited to partake in the TRAP Registry to collect the pregnancy and long-term neurodevelopmental outcome of all first trimester TRAP pregnancies not included in the trial (see separate protocol). Principal investigators can download patient information leaflets and informed consent forms in Dutch, English, German, Italian, Spanish and Hebrew from the study website (www.TRAPISTtrial.eu).

5.3. Withdrawal criteria.

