Intact survival rate defined as the number of surviving infants with normal development at two years corrected for prematurity as assessed by the ASQ® score for infant development. A score of more than 2 SD below the mean score for term-born children will be considered abnormal. Centers that have a follow-up scheme in place, may additionally report the Bayley III score.

Timeframe for assessment: 2 years after expected date of birth

6.2. Methods and timing to assess, record and analyse the efficacy parameters.

	Intervention	Routine visits after intervention	Monthly visits as part of routine follow-up	Birth	Postnatal follow-up	Corrected age of 2 years
Survival and birth at or after 34 weeks	√	√	√	✓		
Need for re- intervention	√	√	√			
PPROM and time from randomization to PPROM	√	√	√			
Miscarriage, time from randomization to birth, birth weight, stillbirth				√		
Neonatal death				✓	✓	
Neonatal complications				√	✓	

Per protocol analysis	√	✓	✓	✓	
ASQ® score					✓
Maternal morbidity	✓	✓	✓	√	

7. Assessment of Safety

7.1. Procedures to record and report adverse events.

All adverse events occurring in women (PPROM, miscarriage, preterm labour), fetuses (intrauterine demise) and neonates (neonatal death and morbidity) must be recorded and are an integral part of the study outcome.

7.2. Definitions.

Adverse Event (AE): Any untoward medical occurrence in a patient or clinical investigation participants undergoing intervention, which does not necessarily have to have a causal relationship with this treatment. An AE can therefore be any unfavourable and unintended sign, symptom or disease temporally associated with the study procedure, whether or not considered related to the procedure.

Serious Adverse Event (SAE): A serious adverse event in the mother is any untoward medical occurrence that results in death or is life-threatening; requires inpatient hospitalization or prolongation of existing hospitalization; results in persistent or significant disability/incapacity.

7.3. Procedures for immediate notification of serious or unexpected adverse events.

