All SAEs that are life-threatening or result in death of the mother must be reported to the promotor within 24 hours. She will perform an initial check of the report, request any additional information, and she will notify it to the steering committee and DSMC. Occurrence of a life-threatening SAE or SAE that results in death of the mother should lead to a meeting of the DSMC who can decide to discontinue the study. All SAE information will be recorded.

8. Statistics

8.1. Description of statistical methods.

The primary analysis will compare the proportion of pump twins who survive the neonatal period and are born at or after 34.0 weeks between the early and late intervention group. The secondary analysis will compare the need for re-intervention, maternal morbidity, time to birth, PPROM and time to PPROM, neonatal and long-term neurodevelopmental outcome between the early and late intervention group. Analysis will be intention to treat.

The following statistical analysis plan is proposed:

Primary outcome	Statistical methods		
Neonatal survival and birth at or after 34.0 weeks	Pearson's chi-squared test [RR, (95%Cls)]		
Secondary outcomes	Statistical methods		
Need for additional interventions	Pearson's chi-squared test [RR, (95%Cls)]		
Maternal Morbidity	Pearson's chi-squared test [RR, (95%Cls)]		
Time from randomization to birth	Log-rank test [HR, (95%CIs)]		
PPROM	Pearson's chi-squared test [RR, (95%Cls)]		
Time from randomization to PPROM	Log-rank test [HR, (95%CIs)]		
Preterm birth <28, <32, <37 weeks	Pearson's chi-squared test [RR, (95%Cls)]		
Gestational age at birth	2-sample student's t-test [mean ± SD]		

Birthweight	2-sample student's t-test [mean ± SD]
Stillbirth	Pearson's chi-squared test [RR, (95%Cls)]
Neonatal death	Pearson's chi-squared test [RR, (95%Cls)]
Severe neonatal morbidity	Pearson's chi-squared test [RR, (95%Cls)]
Per protocol analysis	Pearson's chi-squared test [RR, (95%Cls)]
Abnormal ASQ® score	Pearson's chi-squared test [RR, (95%Cls)]

Multivariate logistic regression will be done to adjust for the GA age strata used as a balancing factor at randomization¹⁹. Because this is a small trial, multivariate logistic and Cox regression may also be used to adjust for any imbalances between the 2 groups at baseline. Possible confounders are maternal age, BMI, parity, mode of conception, socio-economic class, previous history of preterm birth, smoking, and chronic maternal disease.

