An interim analysis by the data safety and monitoring committee (DSMC) will be performed at 33% (n= 40) and 66% (n=80) of enrolment. The O' Brien-Fleming rule will be used to stop the trial early for efficacy. More specifically, if 34 weeks after recruitment and end of the neonatal period of the 40^{th} patient, there is a difference between the 2 groups in the proportion of pump twins that survive and are born at or after 34.0 weeks that reaches a significance of P<0.0005, then the trial will be stopped early. Similarly, if 34 weeks after inclusion of the 80^{th} patient, there is a difference in the primary outcome between the 2 groups that reaches a significance level of P<0.014, then the trial will be stopped early (O'Brien-Fleming stopping rule for efficacy). If the conditional power is less than 10% at one of the 2 interim analyses, the trial will be stopped early for futility. In other words, if the probability of achieving a statistical significant result is less than 1 in 10, the trial will be discontinued for futility.

8.2. Expected number of subjects to be included.

To detect a difference of 25% in neonatal survival and birth at or after to 34.0 weeks between the early (75%) and late (50%) intervention groups, 58 women will need to be included in each arm to achieve at least 80% power at a significance level (alpha) of 0.05 using a Pearson's chi-squared test.

Since we intend to perform 2 interim analyses, the P-value must be set at 0.045 according to the O' Brien-Fleming stopping-rule for efficacy to correct for multiple comparison. Therefore, to detect a difference of 25% in neonatal survival and birth at or after 34.0 weeks between the early (75%) and late (50%) intervention groups, 60 instead of 58 women will need to be included in each arm to achieve at least 80% power at a significance level (alpha) of 0.045 using a Pearson's chi-squared test.

In view of the short follow-up time (28 days after the expected date of birth), we expect the loss-to-follow up rate to be maximum 5% (n=6). To account for this potential 5% loss-to-follow-up rate, the sample size must be increased to 126 patients (120/0.95).

8.3. Criteria for completion of the trial.

The trial will be completed as soon as 63 patients are included in each arm, or earlier if requested by the DMSC. Completion of the trial will be announced on the study website (www.TRAPISTtrial.eu).

8.4. Potential pitfalls.

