TRAP is a rare condition (1 in 35000 pregnancies), so recruitment may be slow. However, if we collaborate with other major fetal medicine centers in Europe, Canada and Israel, this would mean that each year about 100 cases are evaluated. Taken into account that only half will be eligible or willing to participate, it is expected that 3 years of study recruitment will be necessary.

Estimated differences are based on small case series and may be over-optimistic, survival rate may be higher in the late intervention group or lower in the early intervention group and the study may be underpowered to show smaller but still clinically meaningful differences. As such a 10% difference in the primary outcome (60% versus 50%) would still be clinically important, but would require the inclusion of 388 women in each arm, which is not feasible in view of the rarity of TAPS. Nevertheless, even if the study fails to show a significant difference, it will provide information on the 2-year neurodevelopmental outcome of the children, which so far has never been documented for this condition.

8.4. Selection of subjects to be included in each analysis.

The analysis will include all the subjects that have been randomized. All the analyses will be performed by intention-to-treat.

9. Direct Access to Data Source

During the course of the trial, only the members of the DSMC will have direct access to the electronic Case Report Forms (CRF) (www.sealedenvelope.com) in order to perform the interim analyses, monitor data acquisition and quality, and safeguard the patient's safety. At the end of the trial, the DSMC will blind the database for the outcome adjudication (removal of group identifier, gestational age of treatment and method of treatment).

10. Quality and Control Assurance

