This is an academic non-sponsored multi-centre study that is initiated by the steering committee and does not provide funding for either of the 2 study arms. The study will not carry any additional costs to the patients next to what they incur when they are referred for TRAP treatment. Patients will not be paid or reimbursed for participation in the study. All Belgian patients participating in the trial are insured during their enrolment by the sponsor in accordance with Article 29 of the Belgian law related to experiments on humans, 7th May 2004.

Insurance details:

VanBreda risks and benefits [name] Belgium

www.vanbreda.be

Contract Number: 299.053.700

Sites participating in the study will at least be liable for clinical negligence and other negligent harm to individuals taking part in the study and covered by the duty owed to them by the sites concerned, without prejudice to any other liability in accordance with national legislation. Individual sites participating in the study have to arrange their own insurance or indemnity in respect of these liabilities.

14. Publication policy

The promoter takes the commitment of publishing the results of the study. The steering committee together with a statistician ([name]) will write the manuscripts. The first manuscript will deal with the primary outcome and most secondary outcomes, whereas the second manuscript will report on the secondary outcome of 2-year neurodevelopmental delay and intact survival. The steering committee and all principle investigators who contributed by randomizing patients will be co-authors of both manuscripts as part of the TRAPIST-consortium. All investigators must commit that none of the data collected in this trial will be reported separately prior to the publication of the study. Results will be presented to a relevant fetal medicine forum or media only after acceptance of publication. After publication, a summary of the results will be published on the study website (www.TRAPISTtrial.eu)

15. Miscellaneous

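### The 2-year outcome is defined as intact survival, but the section 8.1 table tests only abnormal ASQ, which does not count death as a failure

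*Protocol*

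**What the plan says.** Section 4.1 gives the 2-year outcome as "Intact survival rate (proportion) defined as the number of surviving infants with normal development at two years of age corrected for prematurity", assessed by the ASQ. Section 6.1 repeats the definition: "Intact survival rate defined as the number of surviving infants with normal development at two years corrected for prematurity".

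Section 8.1 introduces its table as the proposed statistical analysis plan. The only 2-year row is "Abnormal ASQ® score", with Pearson's chi-squared test, a risk ratio and a 95% confidence interval. No row is labelled intact survival, and the row names no denominator. Stillbirth and neonatal death have rows of their own; miscarriage and death after the neonatal period do not.

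Three other places bear on the row:
- Section 4.7 says the ASQ is obtained "at 2 years of age corrected for prematurity of the surviving children".
- Section 8.4 on selection of subjects says: "The analysis will include all the subjects that have been randomized".
- Section 14 assigns to the second manuscript the "secondary outcome of 2-year neurodevelopmental delay and intact survival".

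**The concern.** Abnormal ASQ is not the complement of intact survival. A pump twin that dies is neither intact nor abnormal, so the tabulated variable and the defined endpoint differ by exactly the deaths. In this trial deaths are expected to be common and to differ between arms: section 2.1.1 cites up to 33% loss of the pump twin between diagnosis and an intervention at 16 weeks, and section 3 makes preventing those losses the hypothesis.

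An analyst who follows the table must choose one of two denominators:
- **Survivors only.** The comparison is conditioned on an outcome of treatment. The groups compared are no longer those formed by randomisation, and the result conflicts with the all-randomised rule in section 8.4.
- **All randomised.** A dead twin falls among the not abnormal, which favours the arm with more deaths.

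Neither answers the question in sections 4.1 and 6.1. Section 8.4 on potential pitfalls presents the 2-year outcome as something the trial will deliver even if the primary comparison is not significant. In an open-label trial, the test and coding for it should not be left to be settled late.

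**Working it through.** **The plan's own figure.** The only sample size is for the primary outcome, "between the early (75%) and late (50%) intervention groups". With a two-sided test, pooled variance and no continuity correction:

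n = [z(α/2)·√(2p̄q̄) + z(β)·√(p₁q₁ + p₂q₂)]² / (p₁ − p₂)², with p̄ = 0.625

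- α = 0.05: [1.960 × 0.6847 + 0.842 × 0.6614]² / 0.0625 = 57.7, so 58 per arm.
- α = 0.045: [2.005 × 0.6847 + 0.842 × 0.6614]² / 0.0625 = 59.5, so 60 per arm.

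Both agree with section 8.2. No planning figure is given for the 2-year outcome, so the rest uses assumed inputs.

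**Assumed inputs**
- 2-year survival, set A: 75% early, 50% late. These are the primary planning rates used as a stand-in. Section 2.1.1 also puts survival under late treatment at about 50%.
- 2-year survival, set B: 80% early; late 0.67 × 0.80 = 53.6%. The 80% is the protocol's figure for twins that reach 16 weeks and are then treated. Using it for the early arm assumes that early treatment prevents the early losses and does no worse afterwards.
- Abnormal ASQ among survivors: 10% in both arms, range 5% to 20%. The nearest figure in the protocol is 0 of 15 in one cohort (section 11).

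**Formulas.** With survival s and abnormal rate a among survivors: intact survival = s(1 − a); abnormal over all randomised = s·a; abnormal among survivors = a.

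| Quantity (a = 10%) | Set A, early vs late | Set B, early vs late |
|---|---|---|
| Intact survival, all randomised | 0.75 × 0.90 = 67.5% vs 0.50 × 0.90 = 45.0%; RR 1.50 | 0.80 × 0.90 = 72.0% vs 0.536 × 0.90 = 48.2%; RR 1.49 |
| Abnormal ASQ, survivors | 10% vs 10%; RR 1.00 | 10% vs 10%; RR 1.00 |
| Abnormal ASQ, all randomised | 7.5% vs 5.0%; RR 1.50 | 8.0% vs 5.4%; RR 1.49 |

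**Power.** With 60 per arm and two-sided α of 0.05, power for intact survival under set A is about 70% (76% at 5% abnormal, 59% at 20%). Under set B it is about 76% (82% to 64%). When the abnormal rates are equal, the survivor-only test has no power beyond its type I error.

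**Whole-number examples.** Set A, 60 per arm, 45 against 30 survivors, Pearson chi-squared without correction:

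| Abnormal, early vs late | Intact survival | Abnormal, survivors | Abnormal, all randomised |
|---|---|---|---|
| 5 vs 3 | 40/60 vs 27/60, p = 0.017 | 11.1% vs 10.0%, RR 1.11, p = 0.88 | 8.3% vs 5.0%, RR 1.67, p = 0.46 |
| 7 vs 3 | 38/60 vs 27/60, p = 0.044 | 15.6% vs 10.0%, RR 1.56, p = 0.49 | 11.7% vs 5.0%, RR 2.33, p = 0.19 |

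In both rows the defined endpoint differs at the 5% level and the tabulated variable does not.

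**The case against.** The strongest reply is that the row is shorthand. The text of section 8.1 says long-term neurodevelopmental outcome will be compared, sections 4.1 and 6.1 define that outcome, and a separate analysis plan may settle coding. Section 14 names developmental delay beside intact survival, so abnormal ASQ is a planned measure in its own right. This stands in part: the abnormal-ASQ row is legitimate. But it leaves the other promised measure without an analysis. Nor is this detail merely left for later, since the table fixes a variable that differs from the definition.

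A reader might infer four stronger points, which the protocol does not support:
- **The test would reverse the result.** Reversal here is only a change in direction of the point estimate. It needs either a higher abnormal rate among early survivors or the coding of dead twins as not abnormal, which the protocol does not state. None of the reversed examples is significant.
- **Intact survival has no denominator.** The definition is loosely worded as a number, but section 4.1 labels it a proportion and section 8.4 supplies all randomised subjects.
- **A survival benefit would be hidden from the trial.** The primary outcome includes neonatal survival, and stillbirth and neonatal death are tested separately. What may be missed is confined to the 2-year comparison.
- **Intact survival is the only endpoint of the second paper.** Section 14 names two measures.

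**Conclusion.** The mismatch holds and should be corrected. Intact survival is defined twice and promised for publication, yet the analysis table tests a different variable that counts death as a failure on neither denominator. Under the assumed rates, a difference in intact survival of 22.5 to 24 percentage points (67.5 − 45.0; 72.0 − 48.2 = 23.8) coincides with a survivor-only risk ratio of 1.0. The size rests on assumed 2-year survival and on equal abnormal rates of 10%. The structural point needs neither: whenever survival differs between arms, the two variables measure different things. The primary analysis is unaffected.

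**What to change.** Add a row to the section 8.1 table: intact survival, meaning alive with normal ASQ at 2 years corrected age; denominator all randomised; miscarriage, stillbirth, neonatal death or later death counted as failure; risk ratio with 95% confidence interval. Put the same denominator into sections 4.1 and 6.1.

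State how a missing ASQ in a living child is handled. The 5% loss allowance in section 8.2 is justified by the short follow-up to 28 days after the expected date of birth, so it cannot be taken to cover two years.

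Keep abnormal ASQ as a supporting row, labelled as conditional on survival. Dropping its between-arm comparison is not required.

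The cost is one more analysis row and a few words in two sections. No new visit, instrument or data item is needed.
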